# 1 INTRODUCTION

## 1.1 Overview: Deep Vein Thrombosis, Intermittent Pneumatic Compression and Circulation

Deep Vein Thrombosis (DVT) is a blood clot in a deep vein which occurs when venous blood flow is decreased. Lower extremity DVT requires immediate medical intervention, as it can cause a serious or fatal pulmonary embolus (PE). In the US, DVTs are a leading cause of preventable hospital death, affecting 350,000-900,000 patients and an estimated 60,000-100,000 annual deaths. DVTs are the fifth most common reason for hospital readmission, the third most frequent complication of total joint replacement (TJR), and is associated with an estimated annual cost of \$10 billion.

The risk of DVT is increased in hospitalized patients for a variety of reasons including, chemotherapy, surgery, and any condition that causes a general decrease in mobility. Immobility is one of the easiest modifiable risk factors for prevention of DVT. In fact, one recent study showed patients spend as much as 95% of waking hours in bed while they recover. In fact, DVT is the most feared complication of TJR, with more than 300,000 total hip and 700,000 total knee replacements performed annually in the U.S. Current recommendations for postoperative DVT prevention after TJR include anti-coagulant medications and/or external compression of the lower limb for a minimum of 10-14 days. Since the use of anticoagulants increases the risk of bleeding, if the same level of DVT prevention can be achieved with the use of external intermittent pneumatic compression devices (IPC), patients outcomes could be improved. The degree of enhanced blood flow, particularly in the femoral vein, is particularly important for effective DVT prevention, therefore, it is important to understand the blood flow enhancement efficacy of the available IPC products.

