# 8 ADVERSE EVENT REPORTING

## 8.1 Non-Device-Associated Adverse Events

Adverse events occurring during the enrollment period should be documented by the Investigator in progress notes but will not be collected or analyzed by Recovery Force unless considered serious.

Serious adverse events (SAEs) encountered during study enrollment will be documented by the Investigator and reported to Recovery Force immediately upon discovery. SAEs are defined under current Good Clinical Practice (cGCP) guidelines as events that result in one or more of the following:

- life-threatening illness or injury;
- permanent impairment of a body structure or a body function;
- medically necessary in-patient hospitalization;
- medical or surgical intervention necessary to prevent permanent impairment to body structure or function; or
- fetal distress, fetal death, or congenital abnormality.

SAEs will be reported using an Unanticipated Adverse Device Effects (UADE) form which serves the dual role of capturing pertinent SAE information per industry guidelines and capturing device

information pertinent to medical device standards. Other serious events that affect the rights, safety, or welfare of subjects must also be documented on the UADE form and must be reported immediately to Recovery Force and to the Investigator's IRB according to that IRB's policies.

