## **8.2 Device-Associated Adverse Events**

### **8.2.1 Definition of an unanticipated adverse device effect (UADE) event**

A UADE event, as defined by cGCP guidelines, is any SAE, life-threatening problem, or death caused by or associated with a device (or with the process of evaluating a device) if that SAE, problem, or death was not previously identified in nature, severity, or degree of incidence in the investigational plan or application (including a supplementary plan or application), or any other unanticipated, serious, device-associated problem that relates to the rights, safety, or welfare of subjects or operators using the investigational product system or the comparator product system.

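### The serious-event list in section 8.1 omits participant death and prolonged index stay, and DVT or device reactions judged non-serious have no specified sponsor-level collection or by-group table

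*Combined protocol and SAP*

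**What the plan says.** Section 8.1 (Non-Device-Associated Adverse Events) gives adverse events two destinations. They "should be documented by the Investigator in progress notes", and they "will not be collected or analyzed by Recovery Force unless considered serious". It then states that "SAEs are defined under current Good Clinical Practice (cGCP) guidelines as events that result in one or more of the following". Five criteria follow. Three matter here: "life-threatening illness or injury", "medically necessary in-patient hospitalization" and "medical or surgical intervention necessary to prevent permanent impairment to body structure or function". The other two are permanent impairment and a fetal/congenital item, which is the only place in the list where death appears. A closing clause requires any other serious matter bearing on participants' rights, safety or welfare to go on the UADE form and to be reported at once to the sponsor and the IRB.

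Under section 8.2.1, a UADE "is any SAE, life-threatening problem, or death caused by or associated with a device", provided it was not already identified in the investigational plan, or another unanticipated serious device problem. Section 8.2.2 requires investigators to report UADEs and nothing else.

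Section 4.1.2 warns users about pain, swelling, altered sensation, discomfort and allergic reaction. Section 9.3 lets patients stop using the device for discomfort and says nothing about recording it.

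The planned outcomes (sections 2.2, 2.3 and 7.1) are wear time, steps, time to prepare for ambulation, gait speed, and surveys of comfort, acceptance and ease of use. DVT and PE are not outcomes. Nor are they items that the Research Coordinator is told to ask about at the hospital visits, the twice-weekly calls or the 2-week visit (section 2.4).

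**The concern.** The study title is about reducing DVT risk, and the randomised contrast in hospital is one mechanical prophylaxis device against another. A reader of the final report will want the number of DVT/PE events and device reactions in each group. Under section 8 as written, that count would depend on how each site classified events, and non-serious device reactions would not be in it.

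Two features produce this. First, the 8.1 list is incomplete as a definition: participant death and a prolonged index stay are not on it, so sites must reach them through a general clause. Second, both routes to the sponsor require seriousness, and the device route also requires that the event be unanticipated. The reactions the protocol itself foresees are those least likely to pass. Because few events are expected, one or two left in progress notes could change the safety description of either group.

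**Working it through.** **Step 1. Trace each event type through section 8.**

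| Event | Route available | Reaches the sponsor? |
|---|---|---|
| PE | Life-threatening or hospitalisation criterion | Normally yes |
| DVT leading to readmission | Hospitalisation criterion | Yes |
| DVT found in the index stay, or treated without admission | Intervention criterion, if the site reads it that way; otherwise progress notes | Depends on the site |
| Complication that only prolongs the index stay | General clause on other serious events | Depends on the site |
| Participant death, device-associated and not previously identified | UADE definition | Yes |
| Participant death, not device-associated | Not named in 8.1; general clause | Probably, but not by the list |
| Non-serious device reaction | None in 8.1 or 8.2; comfort survey in part | No |

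The list is deficient in the fourth and sixth rows. Collection is unspecified or left to site judgement in the third and seventh.

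**Step 2. Size of the safety description.** The plan gives no figure for this, so there is none to reproduce. Inputs:
- 150 patients per group (Table 1 and section 2.5).
- 15% dropout (section 7.1), so 150 × 0.85 = 127.5, or about 127 observed.
- Symptomatic DVT/PE rate: not in the documents. A range of 0.5% to 2% is assumed for illustration.

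Expected events per group = 150 × rate, and P(at least one) = 1 − (1 − rate)^150:
- 0.5%: 0.75 events; probability 0.53
- 1%: 1.5 events; probability 0.78
- 2%: 3.0 events; probability 0.95

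Exact two-sided 95% upper bound when no event is seen = 1 − 0.025^(1/n):
- n = 150: 0.0243, or 2.4%
- n = 127: 0.0286, or about 2.9%

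**Step 3. Could the groups be tested?** Approximate power to detect a doubling with 150 per group (two-sided 5%, normal approximation) = Φ((δ − 1.96·SE0)/SE1), where SE0 uses the pooled rate. For 1% against 2%:
- SE0 = √(2 × 0.015 × 0.985/150) = 0.01404
- SE1 = √((0.0099 + 0.0196)/150) = 0.01402
- (0.01 − 0.02751)/0.01402 = −1.249, so power is about 11%

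The same formula gives 7% for 0.5% against 1%, and 17% for 2% against 4%. A test would be uninformative; counts with exact intervals are the appropriate output.

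**The case against.** Several stronger readings are tempting, and the documents do not support them.

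- **A reader might infer that these events go unrecorded.** They do not: progress notes are required, section 10.3 gives the sponsor access to study documents, and section 10.6 keeps source documents for three years. What is missing is collection and analysis as study data.
- **A reader might infer that PE, DVT and death escape reporting altogether.** PE would normally meet a listed criterion. Section 1.1 describes lower-limb DVT as needing immediate treatment because of the PE risk, which favours classing a treated DVT as serious. The general clause in 8.1 is mandatory, and the UADE definition names device-associated death and covers the comparator system too. A death that missed every route is a drafting risk, not a likely outcome.
- **A reader might infer that the prolongation gap covers the whole study.** It covers the index stay, expected to last 48 hours or less. After discharge the hospitalisation criterion works as usual.
- **A reader might infer that the conclusions rest on adherence alone.** Steps, gait speed and preparation time are also hypotheses, and the comfort survey captures some device discomfort.
- **A reader might infer two weeks of substituted IPC.** The substitution is clear only in hospital. At home, Group 1 may have stockings, IPC or no device.

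The quoted collection rule also sits under a heading for non-device events. The device-reaction gap comes from 8.2, so a change to 8.1 alone would not close it. Finally, the CRF and the site protocols in Appendices A and B are not in the text reviewed, so some fields may already exist.

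These points narrow the concern. What stands is the incomplete 8.1 list and the lack of a specified route for DVT judged non-serious and for non-serious device reactions.

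**Conclusion.** The point holds in this limited form. The 8.1 list should name participant death and prolongation of the index stay and does not. Symptomatic DVT that a site does not class as serious, and device reactions that are not both serious and unanticipated, have no assured path into the study data and no planned table by group. The first gap depends on site classification. The second follows from 8.2, with comfort surveys a partial offset.

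The likely number of DVT/PE events is small: 0.75 to 3 per 150 at rates of 0.5% to 2%, which are assumed and not taken from the documents. Even complete capture with no events would exclude only rates above 2.4% with 150 observed, or about 2.9% with about 127. The gain is therefore an honest safety description, not evidence that the devices are equivalent. The primary analyses and the sample size are unaffected.

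**What to change.** 1. In section 8.1, add participant death and prolongation of an existing hospitalisation to the serious-event list.
2. Amend both the collection sentence in 8.1 and the reporting duty in 8.2.2. For both groups, record on the CRF symptomatic DVT/PE and device-related events of any seriousness: skin reaction, pain or swelling, altered sensation, allergic reaction, and falls while wearing the device. Record them at discharge, at the existing twice-weekly calls and at the 2-week visit, using the same questions in each group.
3. In section 7.1, add one table of these events by randomised group, with exact 95% confidence intervals and no hypothesis test. Show beside it which prophylaxis device, if any, each Group 1 patient had at home. Some will have none, and device-reaction counts cannot be read without that information.

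The cost is a few CRF fields, slightly longer calls and one table. No new contact with patients is needed. If the CRF already holds some of these fields, the change reduces to stating so in section 8 and adding the table.

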## **8.2 Device-Associated Adverse Events**

### **8.2.1 Definition of an unanticipated adverse device effect (UADE) event**

A UADE event, as defined by cGCP guidelines, is any SAE, life-threatening problem, or death caused by or associated with a device (or with the process of evaluating a device) if that SAE, problem, or death was not previously identified in nature, severity, or degree of incidence in the investigational plan or application (including a supplementary plan or application), or any other unanticipated, serious, device-associated problem that relates to the rights, safety, or welfare of subjects or operators using the investigational product system or the comparator product system.

### **8.2.2 Reporting of device-associated adverse events**

The Investigator will be responsible for reporting any UADEs to Recovery Force and to the Investigator's reviewing IRB. UADEs will be documented by the Sponsor on UADE forms.

# **9 RISK ANALYSIS**

## **9.1 Potential Risks of the Investigational Product and Clinical Investigation**

All subjects will be entering the study voluntarily and the nature of this study should involve minimal risk for study subjects. The only anticipated risks include the possibility of discomfort with the use of the RF MAC Device and potential for feeling uncomfortable with legs exposed during the data collection process. There is also potential for lack of patient satisfaction with the device.

## **9.2 Potential Benefits of the Investigational Product and Clinical Investigation**

It cannot be promised that you will receive any medical benefits from being in this study.

## **9.3 Minimization of Risks**

Patients who experience discomfort with the device can discontinue use immediately to avoid further discomfort.

## **10 INVESTIGATOR RESPONSIBILITIES**

### **10.1 Site Qualification and Study Oversight**

The PI is responsible for general administration of the study. Before the study, the PI must:

- Sign the Protocol Signature Page
- Provide financial disclosures to Recovery Force, per Title 21CFR 54 (see **Section 12.4** below).

During the study, the PI must ensure that:

- The study is conducted ethically;
- Case report forms (CRFs), including Subject informed consents, are provided with each transfer of data requiring informed consent; and
- All other study forms are completed as outlined by this study protocol.

In the case of completion or termination of the study or an Investigator's role in the study, all study materials must be returned to Recovery Force.

### **10.2 Case Report Forms/Electronic Data Records**

As used in this protocol, the term CRF should be understood to refer to either a paper form or an electronic data record or both, depending on the data collection method(s) used.

Original CRFs are the sole property of Recovery Force and should not be made available in any form to third parties, except for authorized representatives of Recovery Force or appropriate regulatory authorities, without written permission from Recovery Force.

It is the PI's responsibility to ensure completion, review, and approval of all CRFs. CRFs must be signed by the PI or by an authorized staff member. These signatures serve to attest that the information contained on the CRFs is true. At all times, the PI has final personal responsibility for the accuracy and authenticity of all clinical and laboratory data entered on the CRFs.

### **10.3 Access to Source Documents**

Recovery Force or its agents and appropriate regulatory authorities shall be granted direct access to all study-related documents to perform verification that the protocol and all applicable Good Clinical Practices (GCPs), and regulations are being followed and to confirm that study documents are complete and accurate. It is important that Investigator(s) and their relevant personnel be made available during monitoring visits and any audits or inspections, and that sufficient time is allotted for the process.

## **10.4 Financial Disclosure**

Investigators must provide Recovery Force with sufficient, accurate financial information in accordance with local regulations to allow Recovery Force to submit complete and accurate financial certification or disclosure statements to the appropriate health authorities. Investigators are responsible for providing information to Recovery Force concerning their relevant financial interests during the course of the study and for one year after completion of the study. Conflicts of interest should be disclosed as required by law.

Recovery Force is the sponsor of this study. This study is funded by a Phase II SBIR awarded to Recovery Force from the National Institutes of Health, National Heart, Lung and Blood Institute (R44-HL132624-02).

## **10.5 Deviations from the Study Protocol**

An Investigator may not deviate from the study protocol without prior approval by Recovery Force unless the deviations are necessary under emergency circumstances to protect the rights, safety, or well-being of human subjects or the scientific integrity of the clinical investigation. These deviations must be documented and promptly reported to Recovery Force and, if applicable, to the IRB providing oversight of the study. Protocol deviations may result in corrective and preventive actions and/or disqualification of the Investigator.

## **10.6 Record Retention**

To enable evaluations and/or audits from regulatory authorities or Recovery Force, the PI and all sub-investigators agree to retain all study records, including copies of all CRFs, UADE forms, and source documents, for three (3) years following completion of the project dependent upon the study data. The Investigator must obtain written permission from Recovery Force before disposing of any records, even if retention requirements have been met.

If an Investigator relocates, retires, or for any other reason withdraws from the trial, Recovery Force must be notified in advance, and study records must be transferred to a designee acceptable to Recovery Force. This designee might be another Investigator, another institution, or Recovery Force itself.

## **10.7 Publication Policy**

The results of this study may be submitted for publication to a medical journal. The PI agrees that any publication of data from this study will comply with Recovery Force publication policy, the instructions to authors outlined by the editor of the journal or conference proceedings where the data is to be published, and the spirit of recommendations made in the good publication practice guidelines (GPP3) of the International Society of Medical Publication Professionals. Recovery Force has the right to review any manuscripts, presentations, or abstracts that originate from this study or that utilize these data before they are submitted for publication or other means of communication.

## **11 ETHICS AND COMPLIANCE**

### **11.1 Investigational Device Exemption**

Although exempt from IDE regulations as noted in Title 21 CFR 812.2(c), the conduct and performance of this study will be in accordance with applicable Recovery Force and Investigator responsibilities as described in Title 21 CFR 809 and Title 21 CFR 812.

### **11.2 Informed Consent and De-Identification**

#### **11.2.1 Prospectively collected data**

All subjects will be given a copy of the IRB-approved informed consent form (ICF) to review before their study participation begins. The Research Coordinator will explain all aspects of the study in lay language and answer all of the potential participant's questions regarding the study. If the participant decides to participate in the study, s/he will be asked to sign and date the ICF. Subjects who refuse to participate or who withdraw from the study will be treated without prejudice.

### **11.3 IRB Review**

The PI is required to obtain IRB oversight of the research study. The IRB must be provided with the Recovery Force-approved study protocol. Performance of the study may not begin until written evidence of IRB approval has been provided to Recovery Force.

The conduct and performance of this study will be in accordance with applicable Recovery Force and Investigator responsibilities as described in Title 21 CFR 812 and other Good Clinical Practice guidance.

IRB/Ethics Committee oversight will be required as human subjects or data from humans are being used. This protocol and the associated informed consent document(s) (if applicable) must be submitted to the IRB for review and approval. Performance of the study at a given site may not begin until written evidence of IRB oversight has been provided to Recovery Force study manager. IRB Review and approval must comply with Title 21 CFR 812 Subpart D.

### **11.4 Confidentiality of Data and Patient Records**

All patients who are enrolled will be assigned an identification number. A list of participant names and their corresponding medical record numbers and participant identification numbers will be kept in a password protected file. Only the research team members and Principal Investigator will have access to this information.

#### **11.4.1 Provisions to Protect the Privacy Interests of Participants**

The PI and/or study institution shall provide sufficient information to allow the IRB to evaluate the researcher's provisions to maintain the confidentiality of data.

Privacy data will be maintained in accordance with HIPAA and other applicable policies and local law.
